- 1) Descriptive analyses (frequency tables) will present, by month, the absolute numbers of contraceptive counseling visits, LARC consultations (with a scheduled insertion) (overall, and by LARC type [contraceptive implant, IUD]); and initiations (overall, and by LARC type [items 1-3 above]).
- 2) Descriptive analyses will present the proportion of LARC initiations out of the number of contraceptive counseling visits [item 4], contraceptive initiations for all methods [item 5], and telehealth-based LARC consultations [item 6]. A consultation is defined as a visit for which a LARC initiation was

scheduled. These analyses will be presented in frequency tables.

3) For each of the uptake outcomes listed above [items 4-7], bivariate statistical analyses will compare the outcome proportions for contraceptive implant vs. IUD, using Chi-square tests.

Aim 1.2 Bivariate analyses will assess the uptake of LARC methods (overall, and contraceptive implant vs. IUD) by patient subgroup, examining LARC initiation (in absolute numbers, and as a proportion of telehealth consultations) by patient characteristics (age, race/ethnicity, gender identity, sexual orientation, sexual activity in last 90 days, gravidity, parity).

Statistical Methods (Aim 1.2)

Bivariate Chi-square tests will compare the proportion who initiated out of those who had 1) a telehealth contraceptive counseling consultation and 2) a LARC consultation for which an insertion was scheduled across subgroups defined by age group (using age categories consistent with the CDC's Youth Behavior Risk Surveillance System, ages 13-14, 15-17, 18-19, 20 and older); race/ethnicity (Hispanic + Black, Black non-Hispanic, Hispanic of any other race, non-Hispanic race other than Black); gender identity (female, male, transmale, gender non-conforming); sexual orientation (straight/heterosexual, gay/lesbian, bisexual, asexual); sexual activity (any/no sexual activity in last 90 days); gravidity (any/no pregnancy history); parity (any/no live birth).

Aim 2: Describe the implementation of telehealth-supported long-acting reversible contraception (LARC) service provision in school-based health centers (SBHCs) using mixed methods.

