Additionally, we will use Chi-squared tests to compare continuation (yes, continued/no, discontinued) between LARC types (contraceptive implant vs. IUD) at two time points: 6 months and 12 months post-initiation. Adjusted analyses using logistic regression will be conducted to compare the continuation at 6 and 12 months (yes or no) separately between contraceptive implant and IUD patients, adjusting for covariates (age, race/ethnicity, gender identity, sexual orientation, sexual activity in last 90 days, gravidity, parity). Operationalization of these covariates is outlined in Aim 1.

Power/Sample Size (Aim 3.1):

The study anticipates enrolling 113 patients, with 102 patients included in the continuation analyses for Aim 3 (primary outcome). Our sample size estimates are based on conservative SBHC clinical data from 2018-2019 and from the first seven months of 2019-20 (which was disrupted by both the transition to a new EHR Epic system and school and SBHC closures due to COVID-19); during the July 2018 to January 2020 time period, there were, respectively, 129 LARC initiations (86 contraceptive implant, 43 IUD), and 44 LARC initiations (41 implant, 3 IUD). These sample size estimates are conservative, as the SBHCs have three newly-hired and trained medical providers since the 2019-20 disrupted year.

We anticipate having complete data for the continuation analyses sample size ($n=102$). Using the new Epic EHR, at each visit within the NYP clinical network – the participating study sites in the SBHCs, as well as the emergency department, inpatient and outpatient clinics – the health care provider is required to conduct reconciliation of medications and document it in the Epic EHR. The medical providers ask every patient at every visit what their current contraceptive method is – confirming the presence of the method, and documenting in two places in the EHR (in the contraception and in medications sections). These analyses will be able to assess continuation (presence of the device at a visit) and censoring

(device removal, device removal with re-insertion).

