Adolescents and young adult high school students are the primary study participants. This study will describe in detail the implementation of a hybrid model of telehealth-supported LARC service provision in a network of 6 SBHCs in New York City that serve students who are between the ages of 13 and 22 years. The specific age range of the students was selected because it reflects the age range of students served by the 6 SBHCs. We are limiting our enrollment to high school students because the study is based in SBHCs. We have used the enrollment and retention strategies proposed in this application in our past research.

Patient population. Based on SBHC clinical data from the full academic year (2018-19), we estimate that, over the 12 month cohort there will be 113 telehealth consultations, defined as a visit in which an appointment is scheduled to initiate a LARC methods (Aim 1), and 102 LARC insertions (Aim 2). The SBHC

² This figure represents total number of visits for all patients, including patients receiving mental health care, who have regularly scheduled repeat visits. The average number of visits per year per unique female patient among LARC users is anticipated to be lower.

patient population, as a whole, is 69% Hispanic and 26% Black (not mutually exclusive), with an average age of 16 years. The majority of patients have their visits covered by Medicaid.

Participants will be eligible to participate in the study if they are: 1) an enrolled patient at the participating SBHC; 2) age 13-22 years; 3) female; 4) had a visit at the SBHC during the study period that is coded as a “reproductive health visit” including contraceptive counseling, contraceptive management, and contraceptive method initiation.

For Aims 2 and 3, individuals will be excluded if they: 1) are younger than age 13 years; 2) are older than age 22; 3) are not an enrolled patient of the participating SBHCs; 4) did not initiate a LARC method; 5) are a person without a uterus; 6) are unable to read, speak, and understand either English or Spanish.

5. Recruitment

Aim 2.1: Adolescent Survey Participants:

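### Aim 1.2, LARC consultation denominator only: with about 11 projected non-initiators the Chi-square approximation may be unreliable across four-level factors, and an exact test should be named

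*Combined protocol and SAP*

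**What the plan says.** Section 2, Statistical Methods (Aim 1.2), names one test: "Bivariate Chi-square tests will compare the proportion who initiated out of those who had" either of two denominators, "1) a telehealth contraceptive counseling consultation and 2) a LARC consultation for which an insertion was scheduled across subgroups defined by age group" and further factors. Age is split into "ages 13-14, 15-17, 18-19, 20 and older". Race/ethnicity and sexual orientation also have four levels each, and the fourth such factor is "gender identity (female, male, transmale, gender non-conforming". Sexual activity, gravidity and parity are binary. Aim 1.2 gives no exact test, no Monte Carlo p-value and no rule for merging levels.

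The size of the second denominator is in section 4, Patient population: "we estimate that, over the 12 month cohort there will be 113 telehealth consultations, defined as a visit in which an appointment is scheduled" for LARC initiation. The same sentence projects 102 insertions, and Power/Sample Size (Aim 3.1) repeats 113 and 102. The number of counseling consultations (the first denominator) is not given. Nor are the subgroup sizes, apart from the overall SBHC mix of 69% Hispanic and 26% Black, not mutually exclusive. Sections 3 and 4 restrict Aim 1 to female patients.

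**The concern.** The Chi-square p-value is a large-sample approximation. What governs its accuracy here is the smaller outcome margin, the non-initiators. If about 11 people are spread over four levels, some expected counts must be small. If some levels are nearly empty, one or two missed insertions can produce a small p-value that the data do not support. Uptake by patient group is part of a secondary outcome in a study meant to inform replication elsewhere. A spurious statement that initiation differs by gender identity, for instance, would be an unwelcome product of the test chosen.

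**Working it through.** **Inputs.** 113 scheduled-insertion consultations and 102 insertions (section 4; repeated in section 2). Four factors with four levels each (Aim 1.2). The plan gives no cell-count or power figure for Aim 1.2, so there is none to reproduce. It also sets no significance level there; 5% is assumed.

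**Non-initiators.** 113 - 102 = 11, or 11/113 = 9.7%.

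**Expected counts, without assuming subgroup sizes.** A level with n patients has n × 11/113 expected non-initiators. To reach 5 it needs n ≥ 5 × 113/11 = 51.4, that is 52 patients, or 5/11 = 45.5% of the total. Three such levels would need 136%, so at most two of four can qualify. With all four levels occupied, at least 2 of 8 cells (25%) fall below 5. The common guide of no more than 20% of cells below 5 therefore cannot be met.

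**Race/ethnicity from the plan's own mix.** Let x% be both Hispanic and Black. The four levels then hold x, 26 - x, 69 - x and 5 + x percent. As x cannot exceed 26, only the 69 - x level can reach 45.5%. At least 3 of 8 cells are below 5 for any overlap, if the network-wide mix applies to these consultations.

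**Actual type I error at nominal 5%.** Subgroup sizes are assumed. The null distribution was enumerated exactly with 11 non-initiators fixed among 113.

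| Assumed split | Chi-square | Exact test |
|---|---|---|
| Four equal groups | 3.7% | 4.7% |
| 62/38/8/5 | 6.0% | 4.6% |
| 108/3/2 (one level empty) | 3.3% | 3.3% |
| 106/4/3 (one level empty) | 7.1% | 3.7% |
| 4/60/45/4 (age) | 9.8% | 4.7% |
| 108/3/1/1 (gender identity) | 20.7% | 1.3% |
| 110/1/1/1 (gender identity) | 26.7% | 2.5% |

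If the number of non-initiators varies binomially instead, simulation gives 6.5% for 4/60/45/4, and 16.8% for 108/3/1/1 against 2.0% for the exact test.

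**What one or two patients can do.** With q = 11/113, the statistic is the sum over levels of (observed - nq)² / [nq(1 - q)], on 3 degrees of freedom.

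- Split 108/3/1/1, non-initiators 10/0/1/0: 0.028 + 0.324 + 9.273 + 0.108 = 9.73, p = 0.021; exact p = 0.21. The patient in the one-person level contributes nearly all of it.
- Same split, the one non-initiator in the three-person level instead (10/1/0/0): p = 0.54.
- Split 4/60/45/4, non-initiators 1/6/4/0: p = 0.67.
- Same split, non-initiators 2/5/4/0: 7.381 + 0.134 + 0.037 + 0.431 = 7.98, p = 0.046; exact p = 0.13.

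**First denominator.** Its size is not given. Assume 150 to 1,000 counseling consultations with 102 initiators. The smaller outcome margin is then 48 to 102, and a level needs only 5/48 = 10.4% down to 5/102 = 4.9% of patients for an expected count of 5.

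**The case against.** The strongest reply is that falling short of a rule of thumb does not show that a test fails. For many assumed splits the Chi-square test stays near its nominal level, and with equal groups it is slightly conservative. The largest errors need levels holding exactly one patient. No gender-identity distribution is given, and in a female-only cohort the male level may be empty and drop out of the table. The figure of 11 is a difference of two projections, and the plan says patient flow will determine the sample. Initiation is also to be examined in absolute numbers, so sparse cells should be visible, and an analyst may well switch to an exact p-value as a matter of routine.

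Most of this stands, and it limits the point. A reader might infer that the Chi-square test is invalid throughout Aim 1.2. The documents do not support that: the 11 belongs to one of two denominators, and the size of the error depends on subgroup sizes that are not given. A reader might also infer that one non-initiator in any small age group would give a significant result. It would not: in a four-patient age level about two are needed.

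What the reply does not remove is that small expected counts follow from the plan's own projections, and that no alternative test is specified.

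**Conclusion.** The point holds for the comparison of initiators out of LARC consultations with an insertion scheduled. On the plan's projections, every four-level factor with all levels occupied has at least a quarter of its expected counts below 5, so the Chi-square p-value may be unreliable. The error is modest for many splits (about 3-7% at nominal 5%), larger for a skewed age split (9.8% for 4/60/45/4), and about 19-27% where levels hold a single patient each.

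This rests on the projected 113 and 102, a 5% level, assumed subgroup sizes, and 11 non-initiators held fixed; letting that number vary lowers the two figures checked (to 6.5% for 4/60/45/4 and 16.8% for 108/3/1/1). The counseling-consultation comparison is much less exposed, although very rare levels could be sparse there too. The analyses concerned are secondary, and the primary continuation test is untouched. This is a minor point, worth acting on because the remedy is so cheap.

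**What to change.** Add one sentence to Statistical Methods (Aim 1.2): subgroup comparisons of initiation out of LARC consultations will use the Fisher-Freeman-Halton exact test or a permutation Chi-square test, as will any other Aim 1.2 comparison in which an expected count is below 5.

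No extra data are needed, and the test keeps its level whatever the subgroup sizes turn out to be. The downside is conservatism when levels are nearly empty: for the assumed 108/3/1/1 split its actual size is 1.3% (2.0% with non-initiators varying), so it has little power there. The absolute numbers that the plan already intends to examine should be shown beside the p-values.

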Aim 2.1 For all patients who initiate a LARC method over the 12 month enrollment period (estimated n=102), we will conduct online follow-up quantitative surveys with all adolescent patients who completed their in-person visit to initiate LARC method (contraceptive implant, IUD) to assess their experience with telehealth-supported care, including: when, where, and using what device they participated in the telehealth video session (e.g. laptop, smartphone, or tablet; with or without headphones); satisfaction with telehealth session (comfort in using telehealth, perceived privacy, extent to which questions were answered); how prepared they felt for the insertion visit; self-efficacy to manage side effects; time (in days) from telehealth visit to method initiation visit; whether attended scheduled follow-up telehealth visit (yes/no); and time (in days) between initiation and follow-up telehealth visit. These surveys will also collect data on interaction with health educators and/or peer health educators. We conservatively estimate a survey sample size of 87 for these surveys (85% participation).

Statistical Methods (Aim 2.1)

Descriptive analyses (frequency tables, means with standard deviations) will describe the telehealth experiences for all survey respondents. Bivariate statistical analyses will compare experiences between contraceptive implant and IUD initiators. We will use Chi-square for dichotomous outcomes, t-tests for means, and Wilcoxon Mann Whitney tests for medians (e.g. time in days between visits).

Aim 2.2 Qualitative interviews with 30 patients, using purposive sampling to ensure a range of perspectives (e.g. age, LARC method, health educator engagement). These qualitative surveys will expand on the aspects covered in the quantitative surveys and will explore, in greater detail, adolescents' experience with the telehealth-supported care from the SBHC, including prior experience with telehealth, perceived benefits and drawbacks of telehealth care overall and for supporting LARC services, specific domains of questions or concerns about side effects and maintenance of their LARC method, and dimensions of youth-friendly care (Ambresin et al., 2013).

Statistical Methods (Aim 2.2)

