This model of enrollment has been successfully used by [name] in prior studies among SBHC patients receiving LARC services (Sangraula et al., 2017).

Quantitative surveys: The quantitative surveys will be programmed into CUIMC-hosted REDCap or Qualtrics, which are HIPAA-compliant. The link to the Initial Survey, with an average of 30-40 questions about the patient’s LARC counseling and insertion appointments, will be sent via text message or email to each participant who provided consent to be contacted. The link to the Follow-Up Survey, with 25-30 questions about the follow-up appointment post-insertion, will be sent via text or email once after the date of their follow-up visit (indicated by the patient in the Initial Survey). Participants who have had their follow-up visit at the time of completing the Initial Survey will be directed to complete the Follow-Up Survey in tandem.

The surveys, survey invitations and reminders, and informed consent forms will be in both English and Spanish; patients can choose which language they prefer to complete the survey. Participants will be sent up to 4 reminders at different times of the day to remind them to complete the survey (over 8 weeks). The English surveys will include, at the end, the option of consenting to be contacted for a follow-up qualitative interview if selected.

Qualitative interviews: Each month, in a phase of 5 per month, a total subset of up to 30 participants will be purposively sampled from the sample who responded to the quantitative survey and provided consent to be contacted for a follow-up telephone or Zoom interview. Given the small sample size, these interviews will be conducted among English-speaking patients (identified by the language in which they completed the survey). Participants will be purposively sampled (using quota sampling) to ensure distribution of respondents across LARC type, age, and race/ethnicity. Interviews will be audio recorded (with the voice print and study number being the only voice data recorded) and transcribed, using only the study ID number.

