Follow-up observation (Continuation Analyses, Aim 3): Follow-up observation will continue for 6 months after the enrollment phase has completed; therefore, participants enrolled in the first month will have 18 total months observation, while those enrolled in the last month will have 6 months. In 2018-19, in the network of 6 SBHCs, 2,425 unique female patients had a total of 12,398 visits (for any purpose), representing an average of 5 SBHC visits per female patient in the academic year.² At each visit to the SBHC, regardless of visit type, all female patients have their medications, including contraceptive method, reconciled and confirmed in the medical record. With the new Epic EHR system, export of all LARC-related procedure codes (insertions, removals, removal with replacement) and device codes (e.g. Nexplanon, Liletta, Paragard) *in addition to all visits* (with corresponding data on current contraceptive method) will enable us to identify person-time events including censoring. At all New York Presbyterian (NYP) sites, the health care provider is required to conduct reconciliation of medications and document it in the EHR at every visit. The SBHC medical providers ask every SBHC patient at every visit what their current contraceptive method is – confirming the presence of the method, and documenting this in two places in the EHR (in the contraception history section, and in the medications section).

Compensation.

All Aim 2 survey and interview participants will receive compensation for their time and effort in the form of an Amazon electronic gift card, purchased through the Mailman School of Public Health. Compensation is as follows:

Quantitative survey participants will receive, as compensation for their time and effort, an Amazon gift card valued at \$10 at the conclusion of the survey. The card will be sent to participants electronically.

Qualitative interview participants will receive, as compensation for their time and effort, an Amazon gift card valued at \$25. The card will be sent to participants electronically.

4. Study Subjects

Subject Population Justification:

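### Aim 2.1 takes follow-up attendance and visit intervals from survey respondents only, although the planned EHR export could supply them for every LARC initiator

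*Combined protocol and SAP*

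**What the plan says.** Section 2, Aim 2.1, defines the survey population as follows: "For all patients who initiate a LARC method over the 12 month enrollment period (estimated n=102"). It expects fewer to respond: "We conservatively estimate a survey sample size of 87 for these surveys (85% participation"). Among the things the surveys are to assess are "time (in days) from telehealth visit to method initiation visit" and "whether attended scheduled follow-up telehealth visit (yes/no); and time (in days) between initiation and follow-up telehealth visit". The statistical methods for Aim 2.1 describe all survey respondents and compare implant with IUD initiators. They name no EHR source, no denominator for attendance, and no rule for when a survey was completed.

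Section 3, AIM 2, Quantitative surveys, splits the instrument in two. The Initial Survey covers the counseling and insertion appointments. The Follow-Up Survey covers the follow-up appointment, and its link "will be sent via text or email once after the date of their follow-up visit (indicated by the patient in the Initial Survey"). Up to four reminders run over 8 weeks, and late answers are foreseen: "Participants who have had their follow-up visit at the time of completing the Initial Survey will be directed to complete the Follow-Up Survey in tandem".

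Section 3, AIM 3, Follow-up observation, plans "export of all LARC-related procedure codes (insertions, removals, removal with replacement") and, in the same sentence, adds device codes and every visit. The use stated there is person-time and censoring. Under AIM 2, the paragraph on linkage of survey data with EHR data provides for joining each survey to the record through the study ID.

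**The concern.** Whether patients come back for telehealth follow-up is one of the more informative facts about a hybrid care model. The Background says that findings from Aim 2 will help to modify the model before it is replicated.

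A survey is a weak source for this fact wherever the item sits. In the Initial Survey, a patient who answers before the follow-up visit cannot yet say whether she attended. In the Follow-Up Survey, the item reaches only patients who answered the first survey and gave a date, and the other questions concern an appointment that a non-attender did not have. If missing the visit goes with not answering, the attendance figure is too high.

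For the two intervals the issue is narrower: patients lost to non-response, and dates recalled when the EHR holds them.

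A smaller matter is that some Initial Surveys will be completed before the follow-up visit and some after it, and the plan pools them.

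**Working it through.** **The plan's own figure.** 102 × 0.85 = 86.7, which rounds up to the stated 87. That leaves 102 − 87 = 15 initiators with no survey.

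**What 15 missing patients allow.** Suppose all 87 respondents report attendance and x attended. Attendance among all 102 then lies between x/102 and (x + 15)/102, a width of 15/102 = 14.7 points. As an example, take x = 61:
- The survey reads 61/87 = 70.1%.
- The full-cohort value lies between 61/102 = 59.8% and 76/102 = 74.5%.
- The survey could be up to 10.3 points too high or 4.4 points too low.

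**Unequal response.** The inputs are the plan's 85% overall response, an assumed true attendance a, and an assumed response r among attenders. Response among non-attenders is then s = (0.85 − a·r)/(1 − a), and the survey reads a·r/0.85.

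| a (assumed) | r (assumed) | s | Survey reads | Error |
|---|---|---|---|---|
| 0.60 | 0.85 | 0.34/0.40 = 0.85 | 0.51/0.85 = 60.0% | 0 |
| 0.60 | 0.90 | 0.31/0.40 = 0.775 | 0.54/0.85 = 63.5% | +3.5 points |
| 0.60 | 0.95 | 0.28/0.40 = 0.70 | 0.57/0.85 = 67.1% | +7.1 points |
| 0.70 | 0.95 | 0.185/0.30 = 0.62 | 0.665/0.85 = 78.2% | +8.2 points |

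Larger errors need overall response below the plan's 85%. With a = 0.70, r = 0.85 and s = 0.60, the survey reads 0.595/(0.595 + 0.180) = 76.8%, at an overall response of 77.5%. With s = 0.40 it reads 0.595/(0.595 + 0.120) = 83.2%, at 71.5%. If non-attenders responded more often than attenders, the sign would reverse.

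**The two intervals.** Telehealth visit to insertion is complete before any survey is sent, so it does not depend on follow-up; the loss is about 15 patients plus recall error. Insertion to follow-up exists only for attenders, so missing non-attenders cannot distort it; the loss is attenders who do not answer, plus recall error.

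**Survey timing.** A spurious implant–IUD difference equals the shift in ratings after follow-up times the difference between methods in the share answering after follow-up. With an assumed shift of 0.2 to 0.5 SD and an assumed difference of 0 to 30 points, it runs from 0 to 0.5 × 0.30 = 0.15 SD. Against that stands the size of the IUD group. At the historical shares given under Power/Sample Size (Aim 3.1), 87 respondents would include between 87 × 3/44 ≈ 6 and 87 × 43/129 = 29 IUD users.

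**The case against.** The case on the other side is substantial, and several parts of it stand.

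- The Follow-Up Survey is triggered by a date that the patient gives. Confirmed attendance is not a stated condition. A patient who gave a date and missed the visit would still get the link and could answer no.
- Permission for contact is sought at the insertion visit, before follow-up. It is therefore not safe to tie the whole of the 85% to later attendance.
- The survey instruments and the list of EHR fields are attachments that are not part of the documents. The Study Purpose speaks of combining surveys with EHR data to assess satisfaction, and survey linkage is described under AIM 2. The investigators may already intend to take visit dates from the record.
- Aim 2.1 is descriptive, with no hypothesis and no power calculation.

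A reader might infer that attendance is certain to be overstated, or that it would come out near 100% among Follow-Up Survey respondents. The documents support neither: both need assumptions about who answers, and equal response gives no error.

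A reader might also infer that "self-efficacy to manage side effects" necessarily mixes answers from before and after follow-up. That holds only if the item is in the Initial Survey, and the documents do not say where it is.

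What remains is that Aim 2.1 names the survey as the source and respondents as the analysis set. Patients who do not respond, or who give no follow-up date, therefore have no stated route into the attendance figure.

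**Conclusion.** The concern holds as a weakness in data source and denominator, with a possible upward bias in attendance that is not demonstrated. The error is 0 points under equal response and about +3.5 to +8 points under the assumed attendance (60% to 70%) and attender response (90% to 95%) at the plan's 85% overall. None of these response patterns comes from the documents.

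For the two intervals the gain from the EHR is completeness and freedom from recall error; no selection bias tied to missed follow-up is shown.

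The timing of the Initial Survey merits a descriptive check at most. The change is worth making because a better source is already being collected, but it is modest: the aim is descriptive, and the primary continuation analysis in Aim 3.1 is untouched.

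**What to change.** In the Statistical Methods for Aim 2.1, state that three items come from the EHR visit export already planned under AIM 3: attendance at the follow-up telehealth visit, days from telehealth visit to insertion, and days from insertion to follow-up. Use all LARC initiators (about 102) as the denominator for attendance, and say which recorded visit counts as the follow-up visit. Keep the survey for what only patients can report.

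The Grant Reporting Manager, who alone holds the link between EHR number and study number, should compute the attendance flag and the intervals before the de-identified export. The documents do not say whether visit dates survive de-identification.

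As an optional descriptive check, report preparedness for insertion by whether the survey was completed before or after the follow-up visit, and do the same for self-efficacy if that item is in the Initial Survey. Do not limit the implant–IUD comparison to surveys completed before follow-up: that would select early responders and shrink an IUD group that may already be very small.

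The cost is a little extra extraction and a few lines of text. Follow-up visits outside the network would be missed, and separating a no-show from a visit never scheduled may need appointment-status data, which the described export does not mention.
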